# 4.2.2.2 Mesial and distal marginal bone loss on standardized periapical radiographs

The marginal bone loss of the study defect is the change on standardized periapical radiographs between baseline and re-entry (Visit 9), and between crown delivery (Visit 10) and at 12 months after the crown delivery (Visit 12).

#### 4.2.2.2.1 Methods of assessment

VERSION 1.1 22(33)

Intra-oral periapical radiographs will be obtained at baseline, at 5 months (re-entry), at crown delivery and at 12 months after the crown delivery. These radiographs should be taken using device to standardize during course of the study and should image the target tooth and at least 2 mm on either side of the osseous defect. The following standardizing technique will produce repeatable diagnostic quality radiographs with close to identical geometry and image clarity. Once the exposure parameters are selected they should not be changed during the course of the study. Send the image files to the central reading center at each study site for analysis following the instructions.

#### 4.2.2.2.2 Derivation or calculation of variable

Image processing software is used to capture measurements. First, the image of the penny will be used for the conversion of pixels to millimeters for every system. The number of pixels per millimeter is calculated by dividing the measurement of the penny in pixels by the known diameter of a penny of 19.2 mm. If all parameters of the system stay the same from radiograph to radiograph, the image of the penny should only be submitted once. However, if any parts of the system change (i.e. the sensor or capturing device, scanner or capturing software), a new penny radiograph should be submitted.

The measurements are taken from a stationary landmark (e.g. the mesial and/or distal adjacent tooth CEJs) to the crest of and distal marginal bone, to the crest and bottom of osseous defect and to the apex of the longest root of mesial and/or distal adjacent tooth in millimeters.  $Ad_0$  is the root length of distal adjacent tooth at baseline;  $Bd_0$  is the measurement from the CEJ to the crest of distal marginal bone at baseline. All measurements are taken parallel to the long axis of the adjacent tooth.

Subsequent images are logged in and saved to the file. Linear measurements of bone height along root surfaces are made using the same method as the original defect.

Measurements to the root apex taken from baseline images (Ad0, Am0) are used to correct for any geometric distortion (elongation/foreshortening) of subsequent images.

Linear bone change (distal) =  $Bd_0 - Bd_{5m}$ Linear bone change (mesial) =  $Bm_0 - Bm_{5m}$ 

# 4.3 Safety measurements and variables

The methods for collecting safety data are described below.

VERSION 1.1 23(33)

#### 4.3.1 Adverse Events

#### 4.3.1.1 Definitions

The definitions of AEs, ADEs and Serious Adverse Events (SAEs) are given below. It is of the utmost importance that all staff involved in the study are familiar with the content of this section. The principal investigator is responsible for ensuring this.

#### **Adverse Event**

An AE is any untoward and unintended medical occurrence in a subject. This definition does not imply that there is a relationship between the AE and the medical device under investigation. An AE which is possibly related, is one that may have been caused by the medical device, or treatment, however there is insufficient information to determine the likelihood of this possibility.

- Possibly related: temporal relationship of the onset of the event, relative to the use/administration of the medical device, is reasonable but the event could have been due to another, equally likely cause.
- Non-related (unlikely): temporal relationship of the onset of the event, relative
  to the use/administration of the medical device, is not reasonable or another
  cause can itself explain the occurrence of the event.

Ambiguous cases should be considered as possibly related.

#### Adverse Device Effect

An ADE is any untoward and unintended response to a medical device. This definition includes any event resulting from insufficiencies or inadequacies in the instructions for use of the medical device or any event that is a result of a user error. This definition also includes treatment- or procedure-related events. ADEs can only occur from the time of medical device use/administration. Here the event is related to the use of the medical device where there is a probable/definite relationship that the event may have been caused by the medical device, or treatment.

- Probably related: temporal relationship of the onset of the event, relative to the use/administration of the medical device, is reasonable and the event is more likely explained by the medical device/treatment than by any other cause.
- Definitely related: temporal relationship of the onset of the event, relative to the use/administration of the medical device, is reasonable and there is no other cause to explain the event.

Expected post-surgical events (i.e., pain, swelling, bleeding and edema) on the study site within 7 days following surgeries will be excluded from AE/ADE.

#### **Serious Adverse Event**

A SAE is an AE/ADE occurring during any study phase of the medical device that fulfills one or more of the following criteria:

- Results in death
- Is immediately life-threatening
- Requires in-subject hospitalization or prolongation of existing hospitalization
- Results in persistent or significant disability or incapacity
- Is a congenital abnormality or birth defect
- Is an important medical event that may jeopardize the subject or may require medical intervention to prevent one of the outcomes listed above

VERSION 1.1 24(33)

If a non-related AE becomes serious, i.e. fulfilling one or more of the above criteria, action should be taken as for any other SAE.

## 4.3.1.2 Recording of Adverse Events and Adverse Device Effects

At each visit, scheduled or unscheduled, the subject will be asked an open question; "Have you had any health problems since the previous visit?"

All health problems, reported by the subject or found at the clinic visit, where the investigator believes the event "possibly" has been caused by the investigational medical device or treatment, must be recorded in the CRF as AEs, specifying time of onset, action taken, outcome and whether it constitutes a SAE or not. Non-related AEs must be recorded in the CRF together with a short description and whether it constitutes a SAE or not.

All health problems, reported by the subject or found at the clinic visit, where the investigator believes the event "probably/definitely" has been caused by the investigational medical device or treatment, must be recorded in the CRF as AEs and ADEs, specifying time of onset, action taken, outcome and whether it constitutes a SAE or not.

Should a pregnancy occur, it must be reported in accordance with the procedures described in Section 8.2, Pregnancy. Pregnancy in itself is not regarded as an AE unless there is a suspicion that a medical device under study may have interfered with the effectiveness of a contraceptive medication.

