## Procedures for discontinuation

Subjects who discontinue should always be asked about the reason(s) for their discontinuation and the presence of any AEs or ADEs. If possible, they should be seen and assessed by an investigator(s). Ongoing AEs and ADEs should be followed up.

A subject will be classified as lost to follow up only if, he/she has failed to return to the required study visits and his/her dental status remains unknown, despite multiple attempts to contact the subject via telephone, fax, email, certified letter and through subject locator agencies (if allowed per national regulation).

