# 3.4 Method of assigning subjects to treatment groups

Screening numbers will be assigned at day of screening (Visit 1). Subjects at center 1 will receive numbers starting at S101 and subjects at center 2 will receive numbers starting at S201. Subject numbers (subject ID) will be consecutively allocated in series at day of inclusion (Visit 2). Subjects at center 1 will receive numbers starting

VERSION 1.1 19(33)

at 101 and subjects at center 2 will receive numbers starting at 201. Enrollment will continue until 22 subjects at each center have been allocated a subject ID. If a subject discontinues, the subject number will not be reused.

Subjects will be randomized strictly sequentially at enrollment (Visit 2). The randomization schedule will be generated using a validated system under the responsibility of the data management team. The randomization procedure will be concealed. Randomization will be stratified by center and smoking habit, i.e. each center will have 11 subjects in each group A and B, respectively with an equal number of subjects with current tobacco consumption per group. The allocation will be revealed to the clinician only following tooth extraction for ridge preservation.

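### Onset, action taken and outcome are required only for adverse events judged at least possibly related, so AE data completeness depends on a causality call made with likely knowledge of the arm

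*Combined protocol and SAP*

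**What the plan says.** Section 4.3.1.2 makes the required detail depend on the investigator's view of cause. Events thought possibly caused by the device or treatment go into the CRF "specifying time of onset, action taken, outcome and whether it constitutes a SAE or not", and the same list applies to events thought probably or definitely caused by it. For all other events the requirement is shorter: "Non-related AEs must be recorded in the CRF together with a short description and whether it constitutes a SAE or not".

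Section 4.3.1.1 (Adverse Event) gives two alternative grounds for the non-related category. The first concerns timing: "Non-related (unlikely): temporal relationship of the onset of the event" is to be judged not reasonable relative to use of the device. The second is that another "cause can itself explain the occurrence of the event". A tie-break follows: "Ambiguous cases should be considered as possibly related".

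On knowledge of the arm, Section 3.4 states: "The allocation will be revealed to the clinician only following tooth extraction for ridge preservation". Section 3.1.5 (Visit 5) has sutures removed in Group B only, at a visit where AEs are recorded. The synopsis (Study design) and Section 4.2.1.1.1 state masking for examiners and central readers. Neither names the person who assesses AEs.

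**The concern.** The amount of information held on an event should not depend on an opinion about its cause, least of all when the person giving that opinion can know the treatment. Here an event labelled non-related carries less required data than the same event labelled possibly related, and onset, which is one ground for the label, is among the items dropped.

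What is at stake is the ability to take a second look. Suppose non-serious events labelled non-related turned out to be more frequent in one arm. Someone working from the required CRF items could count them and read the descriptions. They could not place them precisely in time after grafting or implant placement, could not see how they resolved, and could not judge whether the label was well founded where it rested on timing. Adverse events are a named safety outcome in the synopsis, and with 44 subjects the events may be few, so the detail in each record matters.

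**Working it through.** The point rests on no figure in the plan, so the check is a comparison of the text.

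**1. Required items by judged relationship (Section 4.3.1.2)**

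| Item | Possibly, probably or definitely related | Non-related |
|---|---|---|
| Time of onset | required | not listed |
| Action taken | required | not listed |
| Outcome | required | not listed |
| SAE status | required | required |
| Short description | not listed separately | required |

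Of the 4 items named for related events, 1 is also named for non-related events, so 4 − 1 = 3 are not required.

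**2. Does the definition use an omitted item?** In part. Section 4.3.1.1 allows the non-related label on either of two grounds. Where timing is the ground, the required record does not hold the supporting fact. Where another cause is the ground, a short description may be enough.

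**3. Who makes the call, and can that person know the arm?** Section 4.3.1.2 gives the call to the investigator. The clinician learns the allocation after extraction (Section 3.4). Only Group B receives a collagen plug and sutures securing it (Section 3.1.3), and only Group B has sutures removed (Section 3.1.5). No masked or independent review of relatedness is described. That the assessor can know the arm is an inference, but a sound one.

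**4. How well do visit intervals date an event?** Subjects are asked about problems since the last visit, so each event falls in an interval. The nominal lengths follow from Sections 3.1.4 to 3.1.12:

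- Visit 3 to 4: 7 days; 4 to 5: 14 − 7 = 7 days; 5 to 6: 28 − 14 = 14 days.
- Visit 6 to 7: 28 days to 2 months, about 1 month.
- Visit 7 to 8: 4 − 2 = 2 months; 8 to 9: 5 − 4 = 1 month.
- Visit 9 to 10: no length stated, and it may contain a second surgery if a two-stage approach is used (Section 3.1.9).
- Visit 10 to 11: up to about 6 months; 11 to 12: 12 − 6 = 6 months.

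Dating is fair in the first month, coarse from then to re-entry, and poor after implant placement.

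**5. Which events are affected?** Serious events called non-related are handled as any other SAE (Section 4.3.1.1, Serious Adverse Event), and the sponsor compiles the necessary information with the investigator (Section 4.3.1.3). The gap is therefore confined to non-serious events called non-related.

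**6. Which analyses are affected?** Section 6.1 gives only default descriptive statistics for each variable. No safety comparison by relatedness, timing, action or outcome is specified. Non-related AEs are still entered, so a count of all AEs by arm does not depend on the label.

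**The case against.** The case on the other side is substantial, and it limits the point.

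- **There are routes to check.** Monitors compare the eCRF with medical records (Section 7.1). Section 5.1 provides validation tests and queries, and says that all source data will be entered. These stand as a partial check. They recover onset or outcome only if the site wrote it down, and an item that was never required need not prompt a query.
- **Doubtful cases are protected.** The tie-break sends them to possibly related, where the full list applies. This stands and narrows the gap to events confidently called non-related, though the same investigator decides what is doubtful.
- **Other data are collected whatever the cause.** Table 1 schedules wound dehiscence at Visits 4 to 8 and photographs at Visits 3 to 12. Section 3.5 requires all medication to be recorded, which covers part of action taken. This also stands, in part.
- **The protocol sets a minimum.** The eCRF is not among the documents and may collect more. If so, the text should say so.

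Two stronger readings are tempting. A reader might infer that a non-related call can never be checked or revised; the verification and query provisions contradict that. A reader might also infer that the trial's safety comparison rests on the call. The documents do not support this either: no comparison by relatedness is planned, and a difference between arms in how events were labelled would still be visible in the recorded events and their labels.

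**Conclusion.** The point holds in a limited form. Section 4.3.1.2 states a rule under which the completeness of AE data depends on a causality judgement, and that judgement is made with likely knowledge of the arm. For non-serious events called non-related, three items required elsewhere are not required, and the judgement cannot be re-examined from the required CRF items alone.

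The conclusion rests on one inference, that the AE assessor can know the arm; the documents do not say so in terms. They also give no expected number of AEs or share called non-related, so the number of records affected cannot be estimated. This is a cheap improvement to data collection. It does not threaten the primary analysis or the overall AE count by arm.

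**What to change.** Replace the sentence on non-related AEs in Section 4.3.1.2 with: *For every AE, whatever its judged relationship, record a description, time of onset, action taken, outcome, relationship and SAE status.* Align the related-event sentences in that section with it, so that one list applies throughout.

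In Section 6, or in the SAP if one is prepared, add that all AEs will be tabulated by arm regardless of causality first, and by causality second.

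The added items are already required for related events, so no new kind of data is introduced. The cost is slightly more data entry for minor unrelated events.

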## 4.3.1.3 Reporting of Serious Adverse Events

#### **Timelines for reporting of SAEs**

Investigators and other study site personnel must inform appropriate Sponsor representatives of any SAE that occurs during the course of the study within one day (i.e., immediately but no later than the end of the next business day) of when he or she becomes aware of it.

The Sponsor representative will work with the Investigator to compile all the necessary information and ensure that the appropriate Sponsor personnel receives a report by day one for all fatal and life-threatening cases and by day five for all other SAEs.

If an AE or ADE becomes a SAE, this and other relevant follow-up information must also be provided to Sponsor within one day for all fatal and life-threatening cases and by day five for all other SAEs.

The Investigator is responsible for informing the ethics committee of SAEs as per local requirements.

SUNSTAR is responsible for informing the regulatory authority of device related SAEs as per requirements.

VERSION 1.1 25(33)

## 5 DATA MANAGEMENT

# 5.1 Data handling

Sponsor or the designee will supply investigative sites with access to electronic case report forms (eCRF) via a web-based electronic data capture system. The eCRF will be completed for each included patient. The completed eCRFs will not be made available in any form to third parties without written permission from Sponsor.

All data from source documents will be entered into the eCRF database. The data entry will be verified by means of double data entry or proofreading by each clinical site. Before database lock, both manual and computerized validation tests will be performed and, if necessary, data queries will be sent to the investigator for clarification. Should questionable data be detected during the validation process, written queries will be raised as result of this validation. The study site personnel are required to resolve any such queries. The eCRFs will be retained for 10 years.

At the end of the study, Sponsor or the representative will perform final validation checks, including central consistency checks, after which Clean File will be declared and the database locked.

### 5.2 Record retention

To enable evaluations and/or audits from regulatory agencies or Sponsor and its representatives, the investigator agrees to keep records in the Investigator's Study File (ISF), including the identification list of the participating patients, all original signed Informed Consent forms, and detailed records of medical device disposition. To comply with international regulations, the investigator should retain the records for 10 years.

VERSION 1.1 26(33)

# 6 STATISTICAL METHODS AND DETERMINATION OF SAMPLE SIZE

# 6.1 Statistical evaluation – general aspects

A comprehensive Statistical Analysis Plan (SAP) may be prepared before database lock. If prepared, the SAP will be kept as an appendix to the Data Management Plan. When using the terminology descriptive statistics it means that number of patients, mean, median, standard deviation, minimum and maximum values will be presented for continuous data and frequencies and percentages for categorical data.

If nothing else is stated, descriptive statistics will be given for each variable in the study and p-values may be complemented by confidence intervals as appropriate. All p-values presented will be two-sided. A p-value less than 5% will be called "statistically significant" but all conclusions will be based on the primary objective and hence multiplicity is accounted for even though careful interpretations are necessary as multiple tests are performed.

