### Study timetable

Estimated date of first subject April 2016 enrolled

Estimated date of last subject

April 2017

completed implant placement

80

Estimated date of last subject completed follow-up period

September 2018

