#### Study design

The study is designed as a randomized controlled clinical trial. Patients will be assigned for ridge preservation of a single extraction socket site to treatment group A (GUIDOR® easy-graft CLASSIC) or group B (Freeze-dried bone allograft (FDBA) with collagen plug).

VERSION 1.1 2(33)

The study will involve a ridge preservation procedure and the follow-up observation period in 12 months after delivery of implant-supported prosthesis. The study randomization key will be opened after completion of re-entry visit of all patients for analysis of the primary endpoint. However, examiners and central reading centers will have to be masked until the end of study.

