#### **Outcome variables**

#### **Efficacy**

#### **Primary outcome variable:**

Linear and volumetric horizontal and vertical bone changes at 4 months

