#### Statistical methods

The primary outcome variables of dimensional horizontal and vertical bone changes will be analyzed by Wilcoxon rank sum test.

The secondary outcome variable assessing new bone formation and residual graft particles, and mesial/distal bone loss will be analyzed by Wilcoxon rank sum test.

VERSION 1.1 4(33)

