# 2 STUDY OBJECTIVES

# 2.1 Primary objective

The primary objective is to assess horizontal and vertical linear and volumetric osseous changes after single tooth extraction and the application of two different ridge preservation techniques, via DICOM data analysis. The changes from baseline to four months will be compared. Radiographic measurements will be obtained from DICOM data files acquired by CBCT imaging.

**Hypothesis**: The treatment group with easy-graft CLASSIC is superior or at least not inferior to the control treatment group (FDBA with collagen plug).

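### The plan defines the primary variable in three ways with no rule across variables, so its claim that multiplicity is accounted for holds as written only for horizontal change alone, and nothing requires this to be settled before the key is opened

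*Combined protocol and SAP*

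**What the plan says.** The primary variable appears in three forms.

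- **Wide.** The synopsis outcome list gives "Linear and volumetric horizontal and vertical bone changes at 4 months". The synopsis objectives and section 2.1 likewise include volumetric as well as linear change. Section 4.2.1.1.1, under the primary outcome heading, describes how volume is measured.
- **Middle.** The synopsis statistics paragraph reads "The primary outcome variables of dimensional horizontal and vertical bone changes will be analyzed by Wilcoxon rank sum test". It uses the plural and does not mention volume. Section 4.2.1.1 also names horizontal and vertical change.
- **Narrow.** The one null hypothesis written out in 6.2.1 concerns mid-buccal horizontal change, with significance at p below 5%. Section 6.3 sizes the trial on horizontal change and calls it the primary outcome variable, in the singular.

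On multiplicity, section 6.1 says that "all conclusions will be based on the primary objective and hence multiplicity is accounted for even though careful interpretations are necessary", and the sentence goes on to acknowledge that several tests are done.

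On timing, 6.1 says "A comprehensive Statistical Analysis Plan (SAP) may be prepared before database lock". Section 5.1 places final validation checks at the end of the study, "after which Clean File will be declared and the database locked". The synopsis says "The study randomization key will be opened after completion of re-entry visit of all patients for analysis of the primary endpoint", and adds that examiners and reading centers remain masked until the study ends.

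**The concern.** Resting every conclusion on the primary objective limits the number of tests only if that objective contains one variable. On the narrow form it does, and the error is 5%. On the other two forms there are two or more tests at 5%, and nothing says whether one success is enough, whether all are needed, or in what order they are read.

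The timing gives this weight. The document that could resolve the conflict is optional. If it is written, it meets its stated deadline even when it is finished after the key has been opened and the primary analysis done. The primary variable could then be fixed with group results known and still comply with the protocol. Continued masking of examiners and readers protects the measurements. It does not protect the choice of which measurement is primary.

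**Working it through.** **1. The plan's own sample size.** Inputs from 6.3: difference 0.7 mm, SD 0.8, alpha 0.05, power 80%. Section 6.1 makes all p-values two-sided.

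n per group = 2 × [(1.960 + 0.842) × 0.8 / 0.7]² = 20.5, against the stated 20. Power at 20 per group by the same normal formula is 79.0%. The plan's figure therefore reproduces for one variable at an unsplit 5%. (The planned Wilcoxon test, simulated with normal data, gives about 75% at 20 per group.)

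**2. Error rate if any one success counted.** This decision rule is assumed. The number of variables depends on which form of the primary is used, and the documents give no correlations, so a range is shown.

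- Independent: two variables 1 − 0.95² = 9.75%; three variables 1 − 0.95³ = 14.3%.
- Correlated, two variables: P(any) = 0.05 + 0.05 − P(both). With bivariate normal statistics this is 0.10 − 0.0093 = 0.0907 at correlation 0.5, 0.10 − 0.0165 = 0.0835 at 0.7, and 0.10 − 0.0296 = 0.0704 at 0.9.

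| Correlation | Two variables, normal theory | Two, Wilcoxon simulated at 20 per group | Three, Wilcoxon simulated at 20 per group |
|---|---|---|---|
| 0 | 9.75% | 9.6% | 13.2% |
| 0.5 | 9.1% | 9.1% | 12.8% |
| 0.7 | 8.3% | 8.3% | 10.9% |
| 0.9 | 7.0% | 7.2% | 8.4% |

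The three-variable simulation at correlation 0 lies below 14.3% partly because that version of the rank test, with a continuity correction, rejects slightly less than 5% of the time on each variable.

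**3. Error rate under other rules.**

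- Horizontal change alone: 5%.
- All must succeed: the joint event cannot be more likely than the test of any one true null, so at most 5%. With two variables and both nulls true it is 0.25% to 3.0% over the same correlations.
- Fixed order, each at 5%, stopping at the first failure: at most 5%.

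**4. The timing gap.** The synopsis timetable estimates the last implant placement (the re-entry visit) in April 2017. Its entry "Estimated date of last subject completed follow-up period" is September 2018. April 2017 to September 2018 is 17 months. Lock follows validation checks after that, so the gap to lock could be longer. The dates are estimates, the table is broken in the available text, and the day on which the key is opened is not given.

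**5. A separate, lesser gap in the linear measurement.** Section 4.2.1.1.2 builds its reference point from the CEJs of the teeth on both sides. Inclusion criterion 5 requires only one neighbouring natural tooth. Section 4.2.2.2.2 allows for one neighbour on periapical films, but the CBCT section does not. The number of such patients is not given. If 1 to 5 per group could not be measured (an assumption), simulated Wilcoxon power for 0.7 mm would fall from about 75% at 20 per group to about 72% at 19 or 60% at 15.

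**The case against.** The strongest defence is that section 6 is the operative statistical section and is settled. Its one written null hypothesis and its sample size both concern horizontal change, and on that reading 6.1 is correct. This stands in part. But no section says that section 6 prevails over the synopsis, whose own statistics paragraph differs. Section 6.2.1 also weakens its own authority: it announces two null hypotheses and writes one, refers to three techniques in a two-arm trial, and gives both four and five months.

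A second defence is that nothing forbids an early SAP, and that 6.1 itself asks for careful interpretation. Both are true. A reader might infer that the SAP is due only after the key is opened. The documents do not support that: database lock is a latest date, and an earlier SAP would comply. What stands is that none need exist before the key is opened.

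A third defence is that the inflated error rates depend on a decision rule the plan never states. That is correct, and they must be read as conditional.

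**Conclusion.** The concern holds. The documents disagree on the primary variable and state no rule across variables, so the multiplicity statement in 6.1 is supported as written only on the horizontal-only reading of 6.2.1 and 6.3. This should be corrected before the key is opened, because a choice made afterwards cannot be shown to be independent of the results.

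The size depends on a rule the plan leaves open: 5% for horizontal change alone, at most 5% if all must succeed, and about 7% to 9.75% (two variables) or 8.4% to 14.3% (three) if any one success counted, for assumed correlations from 0.9 down to 0.

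Two stronger readings are not supported. One is that the trial's error rate is 10% or 14%: no section says that one success suffices. The other is that a sole horizontal primary is the only way to control error: a fixed order or an all-must-succeed rule would also do so, but neither is written down.

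The one-neighbour gap is real but of lower weight. Loss of those patients is not established, since both scans would exist and a single masked examiner reads them.

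**What to change.** By amendment before the key is opened, state one rule in the same terms in the synopsis and in 2.1, 4.2.1, 6.1 and 6.2.1:

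- Name horizontal CBCT bone change from Visit 2 to Visit 8 as the primary variable; it is the one that 6.3 sizes. State how the mid-buccal width in 6.2.1 is located relative to the reference point in 4.2.1.1.2.
- Test vertical and then volumetric change after it in a fixed order, each at 5%, or report both as secondary.
- Correct the five-month time point, the three techniques and the two null hypotheses in 6.2.1.
- As a separate, lesser item, add to 4.2.1.1.2 an origin rule for patients with one adjacent tooth, for example the mesial-or-distal approach of 4.2.2.2.2, applied identically to both scans.

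The cost is wording, one measurement rule and an earlier deadline, with no new visits or scans. Sample size and power for horizontal change do not alter. The downside is that vertical and volumetric change can support a claim only if horizontal change succeeds (fixed order), or lose primary status (secondary).

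Other rules cost more. Assuming equal standardised effects on two primaries, a Bonferroni split gives about 64% Wilcoxon power per variable at 20 per group and needs about 28 evaluable per group. Requiring both to succeed gives about 55% to 68% power at 20 per group, for correlations from 0 to 0.9.

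This fix does not settle the hypothesis in 2.1 that the test product "is superior or at least not inferior to the control treatment group", which has no margin while 6.2.1 tests only for a difference. That is a separate issue.
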